### 5.3.4.2 LDH pre-treatment values- Subgroup

Subjects will be classified according to their presenting Lactate Dehydrogenase (LDH) pre-treatment (screening or C1D1) values above the upper normal range vs. below the upper normal range.

- Best Overall Response, ORR and DCR will be presented in a table. (Overall and by cohort)
- PFS will be provided in a table. (Overall and by cohort)

#### 5.3.4.3 LDH pre-treatment values and prior anti-CTLA4 - Subgroup

- Summary of Subjects prior anti-CTLA4 and elevated pre-treatment LDH and BOR.  
A table of BOR will be included. For each level of response, the number of subjects who received prior-anti CTLA4, and the number of subjects with elevated pre-treatment LDH.
- The following variables will be provided for each subject in a listing.  
Subject ID, Time on Prior PD1(months), Prior anti-CTLA4 (yes/no), Elevated pre-treatment LDH (>ULN) (yes/no)), Pre-study anti-PD1 to study start (months) and Best Overall Response on Study.

### 5.3.5 Interim Analyses

No formal interim analyses are considered in the protocol.

Support material has been provided for the regular meetings during the life of the study.

Safety Assessment Committee meetings are organized every three months (approximately).

Medical Monitoring Meetings are organized regularly (approximately every month).

### 5.3.6 Handling of Missing Data

General imputation method: missing data will not be imputed, and it will be considered as missing values for the analysis.

Specific imputations:

#### Weight

In case a cycle's weight is missing it will be imputed via the LOCF—last observation carried forward—method.

#### Partial dates

Only in case of any incomplete date necessary for the analysis:

- Missing day: day 15th of the month and year indicated in each case will be imputed.
- Missing day and month: day 15th of January of the year indicated.
- If the date is completely missing, no imputation will be performed.

Just in case the previous imputation generated an incoherence considering the rest of dates reported for any subject, the day imputed would be the corresponding day according to the rest of dates for the same subject.

These data imputations are for analysis purpose only and will not be used in listings.

#### TEAEs severity.

If severity is missing, the event will be listed as missing severity but summarized as a CTCAE grade 3.

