5.1.4 Serious AE or Serious SAR

An AE or SAR is considered "serious" (SAE or SSAR) if, in the view of either the Investigator or sponsor, it results in any of the following outcomes:

- Death
- A life-threatening AE
- Inpatient hospitalization or prolongation of existing hospitalization
- A persistent or significant incapacity or substantial disruption of the ability to conduct normal life functions
- A congenital anomaly/birth defect.

Important medical events that may not result in death, be life-threatening, or require hospitalization may be considered serious when, based upon appropriate medical judgment, they may jeopardize the patient or subject and may require medical or surgical intervention to prevent one of the outcomes listed in this definition. Examples of such medical events include allergic bronchospasm requiring intensive treatment in an emergency room or at home, blood dyscrasias or convulsions that do not result in inpatient hospitalization, or the development of drug dependency or drug abuse.

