5.2.2 Severity

AE will be reported at the highest grade experienced. The NCI-CTCAE v 4.03 will be used to describe the event and to assess the severity of AEs. For AEs not adequately addressed in the NCI-CTCAE Version 4.03, Table 5 should be used.

Table 5: Toxicity Grading for AEs Not Covered in NCI-CTCAE (Version 4.03)

Grade 1	Grade 2	Grade 3	Grade 4	Grade 5
Mild; asymptomatic or mild symptoms; clinical or diagnostic observations only; intervention not indicated	Moderate; minimal, local or noninvasive intervention indicated; limiting age-appropriate instrumental activities of ADL*	Severe; medically significant but not immediately life threatening; hospitalization or prolongation of hospitalization indicated; disabling; limiting self-care ADL**	Life-threatening consequences; urgent intervention indicated	Death

Semi-colon indicates “or” within the description

Abbreviations: ADL = activities of daily living.

* Instrumental ADL refer to preparing meals, shopping for groceries or clothes, using the telephone, managing money, etc.

** Self-care ADL refer to bathing, dressing and undressing, feeding self, using the toilet, taking medications, and not bedridden.

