### 5.3.3.2 Treatment Emergent Adverse Events

All TEAEs will be coded to System Organ Class (SOC) and Preferred Term (PT) using the MedDRA dictionary v24.0. or later.

Related Adverse Events to APX005M: adverse events with relationship to study treatment (as recorded on the AE eCRF page, Relationship with APX005M = Related) reported by the investigator and those of missing or unknown relationship.

Related Adverse Events to Radiotherapy: adverse events with relationship to radiotherapy (as recorded on the AE eCRF page, Relationship with Radiotherapy = Related) reported by the investigator and those of missing or unknown relationship.

Serious Adverse Events (SAE): serious adverse events (as recorded on the AE eCRF page, Serious Adverse Event = Yes).

Adverse Events Leading to Treatment Discontinuation: adverse events leading to permanent discontinuation of study treatment (as recorded on the AE eCRF page, Action taken with study treatment = Drug withdrawn).

Adverse Events Leading to Death: adverse event leading to death (as recorded on the AE eCRF page, Outcome = Fatal, as well as AEs of Grade 5).

Immune mediated Adverse Events: immune mediated adverse events (as recorded on the AE eCRF page, Immune mediated adverse event= Yes).

Infusion Reactions and or Cytokine Release Syndrome: are identified based on an AE term coded as 'Cytokine release syndrome' or 'Infusion Reaction'

The constellation of symptoms that comprise an APX005M infusion related reaction or cytokine release syndrome will be described.

The NCI-CTCAE version 4.03 will be used to assess the severity grade of TEAEs.

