### 5.3.3.2.1 TEAEs – Overview

An overall summary table will be provided showing the number of TEAEs, the number, and proportion of subjects who presented:

- Any TEAE.
- Any TEAE grade 3 or higher.
- Any TEAE grade 3.
- Any TEAE grade 4.
- Any TEAE grade 5.
- Any TEAE related to APX005M.
- Any TEAE related to APX005M grade 3 or higher.
- Any TEAE related to APX005M grade 3.
- Any TEAE related to APX005M grade 4.
- Any TEAE related to APX005M grade 5.
- Any TEAE related to APX005M only
- Any TEAE leading to dose reduction (APX005M).
- Any TEAE leading to dose delay (APX005M)
- Any TEAE leading to treatment interruption (APX005M)
- Any TEAE leading to treatment discontinuation (APX005M).
- Any TEAE related to Radiotherapy (applicable to Cohort 3)
- Any TEAE related to Radiotherapy only (applicable to Cohort 3)
- Any TEAE leading to radiation discontinuation (only applicable in Cohort 3)
- Any TEAE Immune Mediated.
- Any TEAE Infusion reaction/ cytokine release syndrome.
- Any Serious TEAE.
- Any Serious TEAE with a fatal outcome.
- Any Serious TEAE related to APX005M.
- Any Serious TEAE related to APX005M with fatal outcome.
- Any Serious TEAE related to APX005M only
- Any Serious TEAE related to Radiotherapy (applicable to Cohort 3)
- Any Serious TEAE related to Radiotherapy only (applicable to Cohort 3)

This information will be presented by cohort and overall.

Separate listings will be produced for:

- TEAEs
- TEAEs excluding events marked as a symptom of CRS/IRR
- Serious TEAEs
- TEAEs leading to APX005M discontinuation
- TEAEs leading to APX005M delay
- TEAEs leading to APX005M reductions
- TEAEs leading to infusion interruption
- TEAEs with fatal outcome
- TEAEs immune-mediated events
- TEAEs marked as a symptom of CRS / IRR

The listings will be sorted by Subject ID.

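### The missing-severity rule has no exception for a fatal outcome, so a death with a blank grade would be tabulated as Grade 3 and Grade 5 incidence can be understated

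*SAP*

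**What the plan says.** SAP 5.3.6 (Handling of Missing Data) starts from a general position: "General imputation method: missing data will not be imputed, and it will be considered as missing values for the analysis". It then lists specific exceptions. The one for TEAE severity reads: "If severity is missing, the event will be listed as missing severity but summarized as a CTCAE grade 3". No condition on outcome or seriousness is attached, and no other section of the SAP or protocol adds one.

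SAP 5.3.3.2 defines adverse events leading to death by two routes: "as recorded on the AE eCRF page, Outcome = Fatal, as well as AEs of Grade 5". Outcome and grade are therefore separate fields, and a fatal outcome is enough to classify an event as leading to death.

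The SAP 5.3.3.2.1 overview reports Grades 3, 4 and 5 on separate rows, for all TEAEs and again for drug-related ones (for example "Any TEAE related to APX005M grade 5"). It also has rows for serious TEAEs with a fatal outcome. SAP 5.3.3.2.2 adds tables by maximum grade per subject and separate tables of TEAEs with fatal outcome. Protocol 5.2.2, Table 5, which covers events that CTCAE v4.03 does not adequately address, equates Grade 5 with death.

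**The concern.** Grade 3 is a cautious default for an ordinary ungraded event. It is not cautious for an event known to be fatal. There the correct grade can be read from the outcome field, and the rule replaces it with a lower one. The same event would then be a death in one output and Grade 3 in another, and in the overview both would stand in the same table.

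Incidence and severity of adverse events by CTCAE grade is a secondary endpoint in Protocol 6.3. With cohorts of 11, 11 and 18, a single event can decide whether Grade 5 incidence is reported as zero.

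**Working it through.** The plan states no figure on this point, so there is none to reproduce. The check has two parts: follow the rule through the outputs, then size one affected subject.

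**Part 1. Three hypothetical TEAEs, all with a blank grade:** (a) Outcome = Fatal; (b) non-fatal but recorded as life-threatening; (c) neither.

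| Count | Rule as written | Exception for fatal outcome only | Exceptions for fatal and life-threatening |
|---|---|---|---|
| Grade 3 | 3 | 2 | 1 |
| Grade 4 | 0 | 0 | 1 |
| Grade 5 | 0 | 1 | 1 |
| Grade 3 or higher | 3 | 3 | 3 |
| Fatal-outcome table | 1 | 1 | 1 |

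As written, event (a) is in the fatal-outcome table and in the Grade 3 count, but not in the Grade 5 count. The last two rows are the same under every version, so the defect is confined to how events are split among Grades 3, 4 and 5.

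**Part 2. Size of one affected subject.** Inputs: planned enrolment of 11, 11 and 18 (Protocol 6.1, SAP 5.1), total 11 + 11 + 18 = 40. These are taken as the Safety population sizes, which is an assumption. If the misplaced event is the subject's only Grade 5 event, Grade 5 incidence falls by 1/n:

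- Cohort 1 or 2: 1/11 = 9.1 percentage points
- Cohort 3: 1/18 = 5.6 percentage points
- Overall: 1/40 = 2.5 percentage points

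The overall figure matters because SAP 5.3.3.2.2 names the total Safety population overall as the denominator for TEAE incidence, even for tables by cohort. Read literally, 2.5 points is what those tables would show.

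The Grade 3 side need not rise by the same amount. The overview row for Grade 3 rises only if the subject has no other Grade 3 TEAE. The Grade 3 category of a worst-grade table rises only if the subject is not already counted there and has no higher-grade event.

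**The case against.** The strongest reply is that the trigger is remote. Severity is in the minimum information required for each adverse event (Protocol 5.3.1). Data are checked for completeness (Protocol 7.6). Fatal events are serious by definition (Protocol 5.1.4), so they carry 24-hour notification and follow-up reports (Protocol 5.3.5). Deaths from disease progression are normally kept out of SAE reporting (Protocol 5.3.4), which shrinks the pool further. All of this stands. It makes the case rare, but it does not make the rule right when the case occurs.

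A reader might infer that the plan hides deaths. It does not. They remain in the overview's fatal-outcome rows, the fatal-outcome tables and listing, and the deaths summary and listing of SAP 5.3.3.3. The event listing also shows the grade as missing, so the mismatch can be traced.

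A reader might also infer that Grade 4 is understated in the same way. The documents support this less well. The protocol counts "A life-threatening AE" among the serious outcomes, and Table 5 describes Grade 4 as "Life-threatening consequences; urgent intervention indicated". But the SAP names only a yes/no seriousness field, so it is not established that the life-threatening criterion can be analysed. Table 5 has limited scope, and for laboratory terms Grade 4 rests on numerical thresholds (SAP Tables 8 and 9). Life-threatening seriousness is a separate judgement of immediate risk of death (Protocol 5.1.3).

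Finally, because SAP 5.3.6 summarizes a missing relationship as related, a death could be shown as a related Grade 3 event. As an effect of imputation, that needs both fields blank on the same fatal event, and the relationship rule is itself conservative.

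**Conclusion.** The point holds for fatal outcomes. Followed exactly, SAP 5.3.6 gives the wrong grade to any fatal TEAE with a blank grade, so Grade 5 incidence can be understated and the grade tables can disagree with the fatal-outcome outputs. It would go too far to say that Grade 5 counts are understated: the documents do not show that any such event exists, and if none does the effect is zero.

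The sizes of 9.1, 5.6 and 2.5 points per affected subject rest on planned enrolment. The true Safety population may be larger, because a treated subject who was not evaluable could be replaced (SAP 2.3.5) yet stays in that population (SAP 3.2); each figure would then be smaller. The Grade 4 extension is conditional on a field that the SAP does not name. The likelihood is low, but the possible result is a misgraded death in a safety table, and it is cheap to prevent.

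**What to change.** Reword the severity rule in SAP 5.3.6 along these lines: *A TEAE with a blank grade is shown as missing in listings; in summaries it is counted as Grade 5 when Outcome = Fatal, and as Grade 3 in every other case.* Apply it to all overview rows and all worst-grade tables.

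If the eCRF or SAE form holds the life-threatening criterion as an analysable field, add that a non-fatal blank-grade event meeting it is counted as Grade 4. Confirm that the field exists before writing this into the SAP.

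Query every blank grade on a serious event before database lock, so that the rule is seldom needed.

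The cost of the Grade 5 part is one sentence and a small change to the derivation, using an outcome field the SAP already relies on. It leaves the Grade 3 default in place for all other events and touches no efficacy analysis. The Grade 4 part costs a check of the data fields first.

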#### TEAEs relationship

If relationship is missing or unknown, the event will be listed as missing or unknown relationship but summarized as related.

### 5.3.7 Reporting Conventions

Descriptive statistics will be reported to 2 decimal places.

Estimated parameters, such as regression coefficients will be reported to 3 decimal places.

Percentages should be rounded to 2 decimal places.

P-values  $\geq 0.0001$  will be reported to 4 decimal places; p-values less than 0.0001 will be reported as " $<0.0001$ ".

Listings will be presented and sorted by subject ID, and cohort, when available, listings will also sort by visit.

### 5.3.8 Study Timelines

Date first subject enrolled: 16-Dec-2019

Date last subject enrolled: 21-Oct-2021

### 5.3.9 Technical Details

The most updated study protocol has been used as a reference for this document.

SAS programs, SAS Logs and SAS outputs generated during the creation of the Statistical Report will be archived in the PIVOTAL's File System.

### 5.3.10 Software

The statistical analysis will be performed using the scientific software SAS® V9.4 or later releases and SAS® Enterprise Guide V7.15 or later releases.

## **7. TABLES, LISTINGS AND FIGURES**

This information has been detailed and collected in an external document with the following file name: APX010 - Statistical Analysis Plan - TFLs v1\_0
